2.1. Primary Objective

To evaluate the safety and tolerability of A3907 in patients with PSC with and without a Clinically Relevant Strictures (CRS) following repeat doses.

2.2. Secondary Objectives

- To evaluate the PK of A3907
- To evaluate the effect of A3907 on bile acid levels
- To evaluate the effect of A3907 on liver health
- To evaluate the effect of A3907 on bile acid synthesis

2.3. Exploratory Objectives

- To explore the effect of A3907 on markers of liver inflammation and fibrosis.
- To evaluate the effect of A3907 on symptoms.
- To explore the effect of A3907 on episodes of cholangitis (for patients with available 12-week data prior to single dosing).

Additional exploratory objectives, Arm 4 only:

- To evaluate the effects of A3907 on survival without a liver transplant.
- To evaluate the effect of A3907 on bile duct function

3. Investigational Plan

3.1. Overall Study Design and Plan

This is an open-label, Phase 2 study to evaluate the safety, tolerability, PK, and PD effects of three (3) dose levels of A3907, 10 mg (Arm 1), 30 mg (Arm 2) administered orally once daily (QD), or 30mg twice daily (BID) in Arms 3 and 4 for 12 weeks in patients with PSC with and without CRS ([Figure 1](#)). Eligible patients must have a clinical diagnosis of large-duct PSC obtained by appropriate biliary imaging, and evidenced by chronic cholestasis of more than 6 months duration. Patients must also have serum bile acids above the upper limit of normal (ULN) at Screening Visit and alkaline phosphatase (ALP) levels $> 1.5 \times$ ULN but $\leq 10 \times$ ULN repeated at least 2 weeks apart for baseline to reflect variability of $< 30\%$. If variability is $> 30\%$, a third ALP level may be obtained to determine the direction of abnormality or document stability. If stable ($< 30\%$ variance) the patient may be enrolled.

Prior to any other study procedures being conducted, the patient will have the nature of the study explained to him/her and be asked to sign an informed consent form (ICF). Informed consent must be obtained prior to any study procedures that do not form a part of the patient's normal care. After signing the ICF, patients will be evaluated for study eligibility. If not fasting at time of consent, patient will return to complete screening assessments after having fasted for 4 hours.

The study will include up to a 2-week Screening Period, followed by administration of a single dose of A3907, followed by a 2-week period to confirm the target exposure is reached before beginning a treatment period of 12 weeks ([Figure 1](#)). There will be a total of 8 scheduled visits during the study (including 1 Screening Visit).

Figure 1: Study Design

*EASL defined MRCP Equivalent of clinically relevant strictures: A biliary stricture on MRI/MRCP with > 75% reduction of duct diameter in the common bile duct or hepatic ducts
BID = twice daily; f/u = follow up; PK = pharmacokinetic; QD = once daily; wks = weeks; EASL = European Association for the Study of the Liver

Enrolment into the treatment arms will be staggered with Arm 2 beginning after at least 3 patients in Arm 1 have completed 2 weeks of treatment and an internal Safety Review Committee (SRC) has reviewed safety and PK data. Enrolment into Arms 3 and 4 will occur concurrently beginning after at least 3 patients in Arm 2 have completed 2 weeks of treatment and an internal SRC has reviewed safety and PK data.

The last dose of study drug will be administered at Week 12 (Visit 7) and the End-of-Study Visit (Visit 8) will take place 14 days later. Patients who prematurely discontinue from the study for any reason will undergo End-of-Treatment procedures at the time of discontinuation and End-of-Study procedures within 14 days after the last dose of study drug. Except for patients that discontinue due to an adverse event (AE), withdrawn or terminated early patients may be replaced, as needed, to ensure 6 patients are enrolled into the 12-week Treatment Period of each treatment arm. The end of the study is defined as the time when the last patient completes their last visit.

3.2. Study Endpoints

3.2.1. Primary Endpoints

The primary endpoint is safety and tolerability as determined by the incidence of treatment-emergent adverse events (TEAEs) through Week 12.

3.2.2. Secondary Endpoints

- PK parameters for A3907 including, but not limited to, maximum observed plasma concentration (C_{\max}) and area under the plasma concentration time curve (AUC).
- Change from Baseline to Week 12 in serum, urine and individual and total bile acid levels.
- Change from Baseline to Week 12 in liver biochemical tests (LBTs): aminotransferases (alanine aminotransferase [ALT] and aspartate aminotransferase [AST]), gamma-glutamyl transferase (GGT), alkaline phosphatase (ALP), and total and direct bilirubin levels.
- Change from Baseline to Week 12 in 7 α -hydroxy-4-cholesten-3-one (C4) and fibroblast growth factor 19 (FGF-19)

3.2.3. Exploratory Endpoints

The exploratory endpoints are:

- Change from Baseline to Week 12 in autotaxin
- Change from Baseline to Week 12 in ProC3
- Change from Baseline to Week 12 in high-sensitivity C-reactive protein (hsCRP)
- Change from Baseline to Week 12 in matrix metalloprotease 7 (MMP7) and matrix metalloprotease 9 (MMP9)
- Change from Baseline to Week 12 in enhanced liver fibrosis (ELF) and Mayo-PSC score
- Change from Baseline to Week 12 in carbohydrate antigen 19-9 (CA 19-9)
- Change from Baseline to Week 12 in liver stiffness as assessed by FibroScan
- Changes from baseline to Week 12 in pruritus using the daily pruritus scores captured via the pruritus numerical rating scale (NRS)
- Change from Baseline to Week 12 in fatigue using the daily fatigue scores captured via the fatigue NRS
- Change from Baseline to Week 12 in sleep disturbance using the daily sleep disturbance scores captured via the sleep disturbance NRS
- Change from Baseline to Week 12 in mood using the daily mood scores captured via the mood Likert scale
- Episodes of cholangitis requiring antibiotic use in the 12 weeks prior to single dosing versus the 12 weeks after dosing

Additional exploratory endpoints, Arm 4

- Change of model for end stage liver disease (MELD) from baseline to Week 12
- Change in endoscopic biliary dilation intervals/ frequency in the 12 weeks prior to single dosing (V2) compared to the 12-week treatment period for those patients who are regularly dilated.

3.3. Treatments

In this 12-week study, A3907 doses of 10 mg and 30 mg QD (Arms 1 and 2, respectively), and 30 mg BID (Arms 3 and 4) in a tablet formulation will be administered orally to 6 patients per arm. These doses are expected to result in exposures predicted to be pharmacodynamically active. Approximately 24 patients are expected to be treated in this study with six patients in each of the four treatment arms of the study.

3.3.1. Treatments Administered

The study includes up to a 2-week Screening Period, followed by administration of a single dose of A3907, followed by a 2-week period to confirm target exposure is reached before beginning a treatment period of 12 weeks. Each patient's PK will be reviewed and, if the systemic exposures do not exceed the highest systemic exposure previously established in the SAD portion of the FIH study (C_{max} of CCI ng/mL or AUC of CCI ng h/mL), the dose will be confirmed and the patient will begin administration of A3907 daily for 12 weeks. If the exposures exceed the highest systemic exposure, the individual patient will be terminated early.

Study drug will be dispensed to the patient at defined intervals from Visit 3 through Visit 7, together with instructions on how to store and take the drug. Study drug administration data, including whether each patient took each dose, will be documented through the Patient Diary and transferred to the study database at each visit.

4. General Statistical Considerations

In general, descriptive statistics will be presented by treatment arm and by visit, as applicable. Continuous data will be summarised using descriptive statistics (i.e., n, mean, standard deviation (SD), or standard error (SE), median, minimum, and maximum). Categorical data will be summarised using the patient count and percentage in each category. Non-zero percentages will be rounded to one decimal place, except 100% will be displayed without any decimal places. For the summary statistics of all numerical variables unless otherwise specified, minimum and maximum will be displayed to the same level of precision as reported up to a maximum of three decimal places. Mean and median will be displayed to one level of precision greater than the data collected up to a maximum of three decimal places. Standard deviation and standard error will be displayed to two levels of precision greater than the data collected up to a maximum of four decimal places. When count data are presented, the percentage will be suppressed when the count is zero to draw attention to the non-zero counts. Unless otherwise specified, all confidence intervals (CI) will be 2-sided and performed using a 5% significance level. Confidence intervals will be

displayed to two levels of precision greater than the data collected up to a maximum of three decimal places. A row denoted “Missing” will be included in count tabulations where specified on the shells to account for dropouts and missing values. The denominator for all percentages will be the number of patients in that treatment arm within the population of interest, unless otherwise specified. Refer to the [Appendix 1](#) for imputation rules for partial and missing AE onset dates as well as partial and missing prior/concomitant medication start and end dates. Data will be displayed in all listings sorted by treatment arm.

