4.1. Sample Size

Due to the exploratory nature of this study, no formal power calculations will be used to determine sample size. Approximately 24 patients will be enrolled with six (6) patients in each treatment arm. To ensure 6 patients are enrolled into the 12-week Treatment Period of each treatment arm, patients that discontinue due to an adverse event, withdrawn or terminated early patients may be replaced as needed.

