5.1. Disposition

Disposition will be summarised for all enrolled patients by treatment arm and overall. The number and percentage of patients who have been enrolled, have been treated (i.e., Safety analysis set), have completed the study treatment, have completed the study, have discontinued from the study treatment, have discontinued from the study, as well as the primary reason for the study treatment discontinuation and the study discontinuation will be tabulated.

Additionally, a summary of the analysis sets will be provided to include the number and percentage of patients in each analysis set by treatment arm and overall. A summary of the analysis sets by treatment arm and country will also be presented. Patient disposition, analysis sets and screen failures will be presented in a listing.

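### The Day 1 exposure check is a ceiling, not a target: 12-week results are conditional on passing it, 24 counts entrants rather than patients treated, and 12-week TEAE percentages are diluted by patients removed

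*SAP*

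**What the plan says.** **The check.** Each patient takes one day of A3907 at the arm's dose, "followed by a 2-week period to confirm the target exposure is reached before beginning a treatment period of 12 weeks" (SAP 3.1; similar wording in SAP 3.3.1, the protocol synopsis and protocol 7.1.1). The decision rule in SAP 3.3.1 confirms the dose "if the systemic exposures do not exceed the highest systemic exposure previously established in the SAD portion of the FIH study". Otherwise: "If the exposures exceed the highest systemic exposure, the individual patient will be terminated early". Protocol 5.5 describes the same lead-in purely as a safeguard against going above earlier exposures.

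**The counts.** SAP 3.3 states: "Approximately 24 patients are expected to be treated in this study with six patients in each of the four treatment arms of the study". SAP 4.1 says "Due to the exploratory nature of this study, no formal power calculations will be used to determine sample size" and ties the six to entry into the 12-week period. To secure that number, "withdrawn or terminated early patients may be replaced as needed". Protocol 7.1.1 and SAP 3.1 also define the six as 12-week entrants.

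**The analysis.** The Safety set is everyone given at least one dose (SAP 4.3.3). Unless a section says otherwise, percentages divide by all patients of the arm in the relevant set (SAP 4). SAP 9.1 shows TEAEs for Day 1 to 14, Day 15 to 112 and overall, and names no special denominator. The 12-week exposure, compliance and baseline 2 outputs (SAP 7.3.1, 7.3.2, 8.2.1, 8.2.2, 9.2) are limited to patients who went on to the 12-week period. SAP 5.1 tabulates the "primary reason for the study treatment discontinuation" by arm.

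**The concern.** Three statements do not match what the design delivers.

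- The purpose claims a target, but the rule tests only a maximum. A reader of a null pharmacodynamic result could take adequate exposure as established when the readable check does not establish it.
- SAP 3.3 gives as treated a number that is defined elsewhere as 12-week entrants. The two differ as soon as one dosed patient is removed and replaced.
- A patient removed after Day 1 stays in the denominator of the 12-week TEAE table but can add almost nothing to its numerator. That lowers the displayed incidence, in one of the period displays of the primary safety outcome, in the direction of better apparent tolerability.

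Removal is foreseen. Protocol 5.4 expects individual PK to vary and notes the change to a tablet, and footnote b of the protocol's schedule of assessments plans a visit for patients stopped after Visit 2 because of high exposure.

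**Working it through.** **1. Purpose against rule.** In SAP 3.3.1 only the two numeric limits are blacked out; the sentence around them is readable. Exposure at or below the limit means continue, and above it means stop. No lower bound appears, so the check can confirm that a maximum is not exceeded and nothing more.

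**2. Counts.** The plan's figure reproduces: 4 arms x 6 = 24. No power formula lies behind it. Let p be the share of dosed patients who exceed the limit. If all of them are replaced, the expected number dosed to fill 24 places is 24/(1 - p). If only Arms 3 and 4 are affected, it is 12 + 12/(1 - p). The chance of at least one removal among the first 24 dosed is 1 - (1 - p)^24. The values of p are assumptions.

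| p | Dosed, all arms affected | Dosed, only Arms 3 and 4 affected | Chance of at least one removal in 24 |
|---|---|---|---|
| 0 | 24.0 | 24.0 | 0 |
| 5% | 25.3 | 24.6 | 71% |
| 10% | 26.7 | 25.3 | 92% |
| 20% | 30.0 | 27.0 | 99.5% |

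**3. The 12-week TEAE denominator.** SAP 9.1 counts events up to 14 days after the last dose. For a patient dosed only on Day 1 that window closes on Day 1 + 14 = Day 15, the first day of the 12-week display, so such a patient adds practically no events to it. Suppose 3 of 6 entrants have an event, a true 50%. With six entrants and 6/(1 - p) dosed, the table shows 3/[6/(1 - p)] = 0.5(1 - p): 47.5% at p = 5%, 45% at 10% and 40% at 20%. In whole patients, one removed and replaced gives 3/7 = 43%, and two give 3/8 = 37.5%.

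**4. Conditioning on exposure.** Assume log-normal first-dose exposure with coefficient of variation CV. Put sigma = sqrt(ln(1 + CV^2)) and z = the normal quantile at 1 - p. The geometric mean of those who continue, relative to all dosed, is exp(-sigma x phi(z)/(1 - p)). For CV 50% and p = 20%: sigma = 0.472, z = 0.842, phi(z) = 0.280, ratio = exp(-0.165) = 0.85.

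| p | CV 30% | CV 50% | CV 80% |
|---|---|---|---|
| 5% | 0.97 | 0.95 | 0.93 |
| 10% | 0.94 | 0.91 | 0.87 |
| 20% | 0.90 | 0.85 | 0.78 |

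These are illustrations. The readable text gives neither the limit nor any CV.

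**5. Differences between arms.** In protocol 5.4 and SAP 3.3.1 the limit reads as common to all arms, while planned daily doses are 10, 30, 60 and 60 mg. Suppose the limit were 1.5 times the geometric mean at 30 mg once daily, with CV 60% (sigma = 0.555). Then 1 - Phi(ln 1.5/0.555) = 23% would exceed it. With dose-proportional exposure the same limit is 4.5 times the 10 mg geometric mean, and 1 - Phi(ln 4.5/0.555) = 0.3% would exceed it. So Arm 1 may lose nobody. Arms 3 and 4, at the highest daily dose, are the most likely to lose patients.

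**The case against.** The best defence has five parts.

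- **The limit is a maximum, and both it and the PK variability are hidden.** This stands. A reader might infer that every arm's 12-week results come from a low-exposure subset, or that half the patients could be removed and 12 dosed per arm. The documents support neither. Half removed would need a limit equal to the arm's own geometric mean, whereas protocol 5.4 reports the highest single-dose exposures separately from the geometric mean. At 5% removed, the group that continues is 95% of patients. Doses in Arms 2 to 4 may also be adjusted on earlier PK (protocol 8.2), which could reduce removals.
- **Replacement adds no bias.** This stands. It is tempting to say that arms are refilled with lower-exposure patients, but replacements face the same criteria and the same limit, so entrants have the same exposure distribution with or without them. Replacement is also optional.
- **Removed patients are not lost.** This largely stands. They remain in the Safety set, their events appear in the single-dose and overall displays, and disposition gives a reason. But no planned safety table shows exceedance by arm, and keeping these patients in the 12-week denominator is what causes the dilution.
- **A target may be redacted, and the PK plan is separate.** This stands as a limit on the point. Redactions in protocol 5.4 could hide a target; if so, it should be stated beside the rule. A reader might also fear that comparing Day 98 with Day 0 PK by arm would hide accumulation, but neither document describes such a comparison, so nothing is claimed about it.
- **Arms of six cannot resolve this.** One patient is 16.7 percentage points, and the study is descriptive. True, but the dilution always runs in the same direction and costs almost nothing to remove.

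**Conclusion.** The point holds as a matter of wording, counting and denominator. As readable, the check is one-sided and cannot confirm a target. Week 12 safety and pharmacodynamic results describe patients whose first-dose exposure was at or below the first-in-human maximum. The 24 and six per arm are entrants to the 12-week period; the number dosed would be about 25, 27 or 30 at assumed removal of 5%, 10% or 20% in all arms, and fewer if only some arms are affected. The default denominator lowers 12-week TEAE incidence by the factor (1 - p).

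This assumes that removed patients are replaced, that the table shells (not available) do not set another denominator, and that the limit is common to all arms. Protocol 7.2.4.1 refers to the arm's own highest exposures; if that governs, the ordering across arms in step 5 need not apply. The size of any exposure shift cannot be determined from the documents and may be close to zero. No conclusion is drawn about whether the clinical rule is appropriate.

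**What to change.** Leave the clinical rule unchanged and amend the text and tables:

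1. **SAP 3.1 and 3.3.1:** describe the two-week period as confirming that exposure does not exceed the first-in-human maximum, or state the target if one exists.
2. **SAP 3.3 and 4.1:** restate 24 and six per arm as patients entering the 12-week period, and say that the number dosed may be higher.
3. **SAP 9.1:** use patients who entered the 12-week period as the denominator for 12-week TEAEs, as the SAP already does for its exposure, compliance and baseline 2 outputs. Label the 12-week tables as patients who passed the exposure check. Keep all dosed patients in the single-dose and overall displays.
4. **Beside the TEAE overview, by arm:** give the number dosed, the number and percentage exceeding the limit with an exact 95% confidence interval, and the number replaced. The interval matters at this size: 0 of 6 still has an upper bound of 1 - 0.025^(1/6) = 46%. The row needs one definition of exceedance. The protocol synopsis joins Cmax and AUC with and, protocol 7.2.4.1 with or; these must be reconciled.
5. **Replacement rule:** reconcile SAP 4.1, which makes adverse-event discontinuations replaceable, with SAP 3.1 and protocol 7.1.1, which exclude them. Protocol 7.2.4.2 states no exception.

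The cost is some rewording and one extra table row from data already collected. The stated counts and the 12-week TEAE percentages may look slightly less favourable.

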4.1. Sample Size

Due to the exploratory nature of this study, no formal power calculations will be used to determine sample size. Approximately 24 patients will be enrolled with six (6) patients in each treatment arm. To ensure 6 patients are enrolled into the 12-week Treatment Period of each treatment arm, patients that discontinue due to an adverse event, withdrawn or terminated early patients may be replaced as needed.

4.2. Randomization, Stratification, and Blinding

Blinding is not applicable since this is an open-label study. All patients will take A3907 administered orally daily at approximately the same time each day. Patients will be assigned to treatment arms via an interactive voice/web response system (IXRS).

4.3. Analyses Set

4.3.1. Screened Set

The screened set will include all screened patients who signed the study informed consent, including screen failures.

4.3.2. Enrolled Set

The enrolled set will include all screened patients who signed the study informed consent and met the study eligibility criteria.

4.3.3. Safety Analysis Set

The safety analysis set will include all patients who received at least 1 dose of A3907 and will be used for all analyses except PK and PD analyses.

4.3.4. Pharmacokinetic Analysis Set

The PK analyses set will consist of all patients who received at least one dose of A3907 and have evaluable PK data (i.e. with no major protocol deviation affecting the PK variables). The PK analysis set will be used for all PK analyses.

4.3.5. Pharmacodynamic Analysis Set

The PD analyses set will include all patients who received at least one dose of A3907 and for whom at least one PD marker can be evaluated. The PD analysis set will be used for all PD analyses.

4.4. Study Day

Study Day 1 is defined as the date of first single dose. The reference date for the calculation of study days will be Study Day 1. For some analysis purposes, study day is calculated as:

Date of assessment – Day 1 +1, for assessments done after first dose of study drug;

Date of assessment – Day 1, for assessments done before the first dose of study drug.

The screening period for the study will be from Day -14 (± 2) to Day 1. The single dose will be administered on Day 1/Visit 2. The 12-week treatment period will be from Visit 3 to Visit 7. The End-of-Study Visit will occur on Visit 8.

4.4.1. Overall Treatment Baseline Value (Baseline 1)

For demographics, TEAE, medical and surgical History, prior/concomitant medications, baseline 1 is defined as the last non-missing assessment prior to the first study drug administration.

For other assessments, unless otherwise specified (as for serum biomarkers, clinical chemistry assessments and urinalysis tests with quantitative results, faecal calprotectin assessments, episodes of cholangitis requiring antibiotic use, endoscopic biliary dilation intervals/frequency and NRS analysis below), the baseline 1 value of a parameter is defined as the last non-missing assessment of that parameter prior to the study drug administration of planned single dose.

For serum bile acid assessments, clinical chemistry assessments and urinalysis tests with quantitative results, baseline 1 is defined as the average of all Screening results and results on the day of the planned single dose if both results are available. Otherwise, baseline 1 will be defined as the last non-missing assessment prior to the study drug administration of planned single dose.

For other serum biomarkers and faecal calprotectin assessments, baseline 1 is defined as the assessment performed on the day of the planned single dose.

For episodes of cholangitis requiring antibiotic use, endoscopic biliary dilation intervals/frequency, baseline 1 is defined as data collected on the day of the planned single dose, which are assessments of 12 weeks prior to Single Dosing.

For NRS analysis, baseline 1 will be calculated by averaging the two weekly scores obtained prior to the day of the planned single dose.

4.4.2. 12-Week Treatment Period Baseline Value (Baseline 2)

For assessments that are interested in the change from baseline 2 during the 12-week treatment period, baseline 2 is defined as the last non-missing value of the assessment prior to the 12-week treatment period.

